A PhD student will be part-time (50%) appointed for this trial. He/she will be accountable for both sites (AZ Sint-Jan Brugge & UZ Leuven). The financial remuneration will be split between Goodlife Pharma and Pro Well. The PhD student will assist with

- Recruitment of patients: The PhD student will have access to the medical records of the patients of UZ Leuven and to the pseudomized data of AZ Sint-Jan Brugge by using Redcap.
- Data collection and monitoring
- Planning and monitoring
- Adverse event reporting
- Scientific report writing and dissemination

Goodlife Pharma

The pharmaceutical company (Goodlife Pharma) will provide the “Study drugs” (MYSIMBA) free of charge. For this multicenter study, Goodlife Pharma will supply the coordinating site (UZ Leuven) as well as the participating site (AZ Sint-Jan Brugge).

Pro Well

The study diet (VLCKD) and lifestyle program will be provided by the Company (Pro Well). For this multicenter study, Pro Well will supply the coordinating site (UZ Leuven) as well as the participating site (AZ Sint-Jan Brugge).

Both Goodlife Pharma as Pro Well

No payments other than those explicitly foreseen shall be made by Company to Institution with respect to the Study, unless agreed in writing. Such agreement must be executed by authorised personnel, must include a specific statement of any fees or costs to be paid and the reasons for payment, and must be attached as an annex to this Agreement.

An overview of the budget is displayed on the next page.

Budget

Items/Staff	Per unit Cost	Quantity	Total
VLCKD	-	-	Provided by Pro Well
Lifestyle program	-	-	Provided by Pro Well
Mysimba tablets	-	-	Provided by Goodlife Pharma
PhD student (50%)	-	-	Split between Pro Well and Goodlife Pharma
Pregnancy test	€ 10.00	20 tests	€ 200.00 by Internal fund (KUL/UZ Leuven krediet)
UZ Leuven			
Study specific lab tests (fasting glucose, lipids)	€ 10.86	62 samples	€ 673.32 by Internal fund (KUL/UZ Leuven krediet)
Pharmacy transit	€ 2,426.40	1 site	€ 2,426.40 by Internal fund (KUL/UZ Leuven krediet)
AZ Sint-Jan Brugge			
Study specific lab tests (fasting glucose, lipids)	€ 21.54	62 samples	€ 1,335.48 by Internal fund (KUL/UZ Leuven krediet)
Start-up fee	€ 250.00	1	€ 250.00 by Internal fund (KUL/UZ Leuven krediet)
Annual fee	€ 100.00	2 years	€ 200.00 by Internal fund (KUL/UZ Leuven krediet)
Pharmacy transit	€ 340.00	1 site	€ 340.00 by Internal fund (KUL/UZ Leuven krediet)
Total			€ 5,425.20

ROLES AND RESPONSIBILITIES

Study rationale	Bariatric surgery induces substantial weight loss and reduction in obesity-related comorbidities. Despite the major benefits of bariatric, some patients still regain weight post-operatively. This is the reason why we want to investigate the influence of a pharmacotherapeutic treatment (naltrexone/bupropion) on weight regain after bariatric surgery. This multicenter, randomized clinical trial will compare the outcomes of two different groups: all participants will receive intensive lifestyle management and naltrexone/bupropion, and one experimental group will in addition follow a very low calorie ketogenic diet (VLCKD).
Primary objective	To evaluate the superiority of combined VLCKD, intensive lifestyle intervention and naltrexone/bupropion versus standard of care with naltrexone/bupropion on weight loss.
Secondary objective(s)	To describe changes in metabolic health parameters and health-related quality of life during combined treatment of VLCKD, intensive lifestyle program and naltrexone/bupropion versus standard of care alone with naltrexone/bupropion.
Study design	Prospective Multicentric Longitudinal Randomized Controlled Study
Endpoints	Primary endpoints • The percentage of weight loss at 26 weeks Secondary endpoints • A weight loss percentage at 10 weeks, 16 weeks and at end of trial (= 52 weeks from start)

	
• A proportion of patients with a weight loss percentage of 5% or more at 10, 16, 26 and 52 weeks• A proportion of patients with a weight loss percentage of 10% or more at 10, 16, 26 and 52 weeks• The time to reach a weight loss percentage of 5% and 10%• The dose of naltrexone/bupropion used at 10, 16, 26 and 52 weeks and at the end of the trial• The tolerability of VLCKD and NB• The adherence to VLCKD and NB• The Patient-Reported Outcome Measures (PROMs) of hunger and cravings at 0, 4, 10, 16, 26 and 52 weeks• The change in fasting glucose, lipids and blood pressure at 10, 16, 26 and 52 weeks
Sample Size	
• Experimental/treatment arm: 31 patients• Comparator arm: 31 patients• Total: 62 patients
Third parties	
• Pro Well
◦ Provide VLCKD◦ Provide Lifestyle program• Goodlife Pharma
◦ Provide Mysimba tablets

STUDY FLOWCHART

Procedures/assessments	Phase 0: Screening and randomization		Phase 1: Lifestyle + NB with vs without VLCKD							Phase 2: Lifestyle + NB (all participants)				Follow-up (all participants)		
	Screening (In-clinic)	Randomization (in-clinic)	Remote	Remote	Remote	Remote	Remote	Remote	In-clinic (study specific)	Remote	Remote	In-clinic (Routine)	Remote	Remote	In-clinic (study specific)	In-clinic (routine)
Visit	V1	V2	V3	V4	V5	V6	V7	V8	V9	V10	V11	V12	V13	V14	V15	V16
Timing of visits (weeks)		Start	Start	W3	W4	W6	W8	W10	W10	W12	W16	W16	W20	W26	W26	W52
Visit window (days)									±30			±30			±30	±30
Lifestyle program			X		X		X			X	X		X	X		
Naltrexone/bupropion (NB)		X							X			X			X	X
VLCKD			(X) ¹	(X) ¹	(X) ¹	(X) ¹	(X) ¹	(X) ¹								
Screening assessments and randomization																
Informed consent	X ²															
Inclusion/exclusion criteria	X	X														
Randomization		X														
Anthropometric data (height, weight, waist circumference)		X							X			X			X	X

Clinical examination (Blood pressure, heart and lung auscultation, abdominal palpitation and percussion)		X							X			X				X	X
Laboratory tests																	
Fasting glucose		X							X			X				X	X
Hemoglobin A1c		X										X					X
Lipids: LDL-cholesterol, HDL-cholesterol, triglycerides		X							X			X				X	X
Liver test: AST, ALT, gamma-GT, alkaline phosphatase, total bilirubin, albumin		X										X					X
Kidney function: creatinine, eGFR		X										X					X
Thyroid function: TSH, free T4		X										X					X
Uric acid		X										X					X
Questionnaires																	
The PsyEndoAUDIT questionnaire ³		X							X			X				X	X
The PsyEndoCIDI questionnaire ³		X							X			X				X	X
The PsyEndoEDE questionnaire ³		X							X			X				X	X
The PsyEndoHADS questionnaire ³		X							X			X				X	X
Nederlandse vragenlijst voor eetgedrag ³		X							X			X				X	X
The ObesitasIPAQ questionnaire ³		X							X			X				X	X

The quality of life (SF-36) questionnaire ³		X							X				X			X	X
The outtake questionnaire															X		
Reason for discontinuation		X							X			X			X	X	
(Serious) Adverse event (S)(AE) assessment		X							X			X			X	X	

- Depending on randomization in either intervention (with VLCKD) or comparator group (without VLCKD).
- Informed Consent must be obtained prior to performing any other Trial-related procedures as part of the standard of care.
- See appendix 4 for the respective questionnaires.

I Background and Rationale

The world-wide prevalence of obesity has increased to the extent where it is considered as an epidemic. According to the World Health Organization (WHO) the population of people with obesity almost tripled in a time period of 40 years. Obesity is a medical condition in which excessive fat accumulation causes secondary health issues. This corresponds clinically to a body mass index (BMI) greater or equal to 30 kg/m².⁽¹⁾

Initially, the patient will be advised to change his/her lifestyle. This includes increasing physical activity as well as being on a diet and behaviour modification. A tailored lifestyle program usually consists out of 2-3 hours of exercise per week. Here, it is especially important to engage in aerobic sports such as walking at a higher than usual pace, cycling or swimming. This ensures that patients use their fat storage as source of energy instead of carbohydrates. Unfortunately, lifestyle modification alone in terms of physical activity will result in only limited short-term weight loss. Therefore, a diet containing of a calorie restriction is an important additional part of the new lifestyle.⁽²⁾

Calorie restriction is an important part of the very low-calorie ketogenic diet (VLCKD). This diet typically consists out of a limited intake of carbohydrates and a daily energy restriction of 800 kcal. Also an increase in protein percentages is favourable in these patients.⁽³⁾ A dietitian is usually appointed for this intervention because VLCKD is an important factor in the possible eligibility for surgery as well as weight loss results after bariatric surgery.⁽⁴⁾ Studies also showed that VLCKD given prior to pharmacotherapy can have an additional benefit. It will help to reset the metabolic state and impose nutritional structure. ^{(5) (6)}

Pharmacotherapy is the last resort for patients before bariatric surgery. The medication used in this trial is naltrexone/bupropion (NB) with extended release. Naltrexone is an opioid antagonist that is currently used in the treatment of dependency, like alcoholism and drug addiction. Bupropion on the other hand is an antidepressant used not only in the treatment of depression but also to reduce cigarette cravings with the ultimate goal of inducing a smoking cessation. A common side effect of bupropion is weight loss. The use of both drugs separately has almost no effect on the patients' weight, but the combination of naltrexone and bupropion has showed a synergistic effect.⁽⁷⁾ NB has promising results in terms of weight loss prior to or post-bariatry with an influence on food intake, cravings and a high sense of satiety.⁽⁸⁾

Conservative therapy may already make a difference, but the majority of patients experience a lack of beneficial effect from this. For these patients, bariatric surgery (BS) may be the solution. Bariatric surgery is considered as the best treatment for morbid obesity (BMI > 40 kg/m² or BMI > 35 kg/m² with one or more weight related comorbidities) in maintaining weight loss.⁽⁹⁾ The biggest weight loss occurs the first year after surgery. Unfortunately, from then on weight stabilization or even weight regain can occur post-bariatry.⁽¹⁰⁾

Despite the fact these patients already tried conservative therapy prior to bariatric surgery, they still benefit to monitor their lifestyle in terms of physical activity, behaviour and dieting. Recent studies show a beneficial role for pharmacotherapy for post-bariatric weight regain.⁽¹¹⁾ Given the mechanism of action of NB, specific benefit can be expected in patients with insufficient reduction or relapse of food cravings and snacking after bariatric surgery. ⁽⁸⁾ Although these possible desirable effects may occur, yet patients may suffer from some side effects of the study drug. The most common adverse events are gastrointestinal disorders (nausea, vomiting, constipation), anxiety, insomnia, agitation and a headache.⁽¹²⁾

Generally, there is a lack of published data on the effectiveness of pharmacotherapies for post-bariatric weight regain. Therefore, this trial aims to investigate a structured follow-up with lifestyle intervention combined whether or not with a VLCKD and supported by naltrexone/bupropion on the evolution of bodyweight in patients with weight regain post-bariatry. This multi-center, randomized clinical trial will compare the outcomes of two different groups. The patients in both groups need to undergo lifestyle changes in combination with the intake of naltrexone/bupropion, but the experimental group needs to follow a VLCKD on top of it for a period of 10 weeks.]

2 Study Design and Objectives

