2.3 Secondary Endpoints

- A weight loss percentage at 10 weeks, 16 weeks and at end of trial (= 52 weeks from start)
- A proportion of patients with a weight loss percentage of 5% or more at 10, 16, 26 and 52 weeks
- A proportion of patients with a weight loss percentage of 10% or more at 10, 16, 26 and 52 weeks
- The time to reach a weight loss percentage of 5% and 10%
- The dose of naltrexone/bupropion used at 10, 16, 26 and 52 weeks and at the end of the trial
- The tolerability of VLCKD and NB
- Adherence to VLCKD and NB
- The Patient-Reported Outcome Measures (PROMs) of hunger and cravings at 0, 4, 10, 16, 26 and 52 weeks
- The change in fasting glucose, lipids and blood pressure at 10, 16, 26 and 52 weeks]

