2.4 Study design

This is a parallel multicentric longitudinal randomized controlled trial in which prospective data will be collected from the electronic health record. The inclusion and exclusion criteria will be checked and afterwards patients will be randomized to (unblinded) medication only or combination with VLCKD. Both groups include NB and lifestyle changes for 26 weeks but the patients belonging to the experimental group must follow a VLCKD in the first 10 weeks on top of it. Like the other group, the remaining 16 weeks will consist of NB combined with lifestyle interventions. Afterwards there is a follow-up extension of 26 weeks. See appendix 4 for detailed overview of clinical and biochemical parameters to be collected during the trial.

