4.5 By visit

There are five scheduled in-clinic visits, each involving a blood draw. Among these, three visits are routine for naltrexone/bupropion, which include the initial intake and visits after 16 and 52 weeks. The study-specific visits occur at 10 weeks and 26 weeks. During the routine visits, only fasting glucose and lipid levels (LDL-cholesterol, HDL-cholesterol, triglycerides) will be assessed in the blood. However, during the study-specific visits, in addition to fasting glucose and lipids, the following parameters will also be examined in the blood: Hemoglobin A1c, liver function (AST, ALT, gamma-GT, alkaline phosphatase, total bilirubin, albumin), kidney function (creatinine, eGFR), thyroid function (TSH, free T4), and uric acid. For a detailed overview of the visit schedule, please refer to the Study Flowchart.

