6.2 Statistical Analysis

[The primary analysis will be performed using a two-sample two-sided t-test to test the difference in mean weight loss percentage between both treatment arms. Mean weight loss percentages and the mean difference in weight loss percentage will be estimated and presented with 95% confidence intervals. A 5% significance level will be adopted for the primary analysis. Given the pragmatic nature of the trial, the primary analysis will be performed following the intention-to-treat (ITT) principle, in that all randomized patients will be analyzed in the study arm in which they were randomized, regardless of adherence to the therapy assigned to the patient. In presence of missing outcome data due to drop-out of patients for whom

no follow-up data were collected, the method of multiple imputation will be used. Fully conditional specification will be used to create 10 complete data sets, of which each will be analyzed and analysis results combined according to multiple imputation principles. Treatment arm and previous weight loss measures will be used as predictors in the imputation model.

A per protocol (PP) analysis will be performed as a secondary analysis, including patients adherent to the randomized treatment. Missing data will be dealt with as described above, using multiple imputation.

Linear mixed models for longitudinal data will be used for the analysis of a treatment effect on weight loss percentage at other time points. The explanatory model will contain treatment arm, time point and the interaction thereof. A random effect for patient will be modelled to deal with data clustering. Results will be presented as mean differences per time point with 95% confidence intervals.

The treatment effect on the proportion of patients with weight loss at various time points will be analyzed using logistic regression analysis, with generalized estimating equations (GEE) to account for data clustering. The explanatory model will contain treatment arm, time point and the interaction thereof. Results will be presented as odds ratios per time point with 95% confidence intervals

The treatment effect on the time to reach a pre-defined weight loss percentage will be analyzed using a log-rank test for time-to-event outcomes. Additionally, a Cox model will be used for the estimation of the hazard ratio with 95% confidence interval.

Descriptive analyses will be used for tolerability or adherence to treatment.]

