Appendix 2: [Pro Well VLCKD protocol]

- BMI 27+ program: 10 weeks
 - 4 weeks VLCKD strict phase: 800 kcal/day (<50g carbs, >100g proteins, vegetables with a low carb content)
 - 3 x 2 weeks of progressive increase of daily kcal: 1000 kcal, 1200 kcal (W) / 1400 kcal (M), 1500 kcal (W) / 1800 kcal (M) based on Mediterranean diet
 - Coaching minutes: 2 hours 15 minutes

Intake	30 minutes	Explanation VLCKD & App
Follow-up 1: after 3 weeks	15 minutes	Follow-up
Follow-up 2: after 4 weeks	15 minutes	Explanation 1000 kcal meal plan
Follow-up 3: after 6 weeks	15 minutes	Explanation 1200/1400 kcal meal plan
Follow-up 4: after 8 weeks	15 minutes	Explanation 1400/1800 kcal meal plan
Outtake after 10 weeks	15 minutes	Progress & Reflection

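### The ±30-day windows at weeks 10 and 16 overlap, and the week-10 window straddles the end of the diet, so the week-10 contrast pools on-diet and post-diet patients.

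*Protocol*

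**What the plan says.** The Study Flowchart has a row "Timing of visits (weeks" that puts V9 at week 10 and V12 at week 16. Below it, the row "Visit window (days" gives ±30 days to each of V9, V12, V15 (week 26) and V16 (week 52). No minimum interval between visits is stated. V9 is the last column of Phase 1, in which the arms differ by the diet. V12 lies in Phase 2, in which both arms have the same scheduled treatment.

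Section 2.4 says that experimental-arm patients "must follow a VLCKD in the first 10 weeks on top of it". Appendix 2 breaks this down as "4 weeks VLCKD strict phase: 800 kcal/day", followed by "3 x 2 weeks of progressive increase of daily kcal".

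Section 4.5 classes V9 as study-specific: "The study-specific visits occur at 10 weeks and 26 weeks". The week-16 visit is described there as routine.

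Section 2.3 lists among the secondary endpoints "A weight loss percentage at 10 weeks, 16 weeks and at end of trial (= 52 weeks from start". It also uses weeks 10 and 16 for the 5% and 10% responder proportions and for changes in fasting glucose, lipids and blood pressure. Section 6.2 models arm, time point and their interaction, and states: "Results will be presented as mean differences per time point with 95% confidence intervals". Odds ratios are likewise reported per time point. The same section uses earlier weight-loss measures as predictors when imputing missing primary outcomes.

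**The concern.** The diet is the only scheduled treatment that separates the arms, and V9 is the only in-clinic measurement of weight, laboratory values and blood pressure planned for its end. A window that is wide relative to the 70 days elapsed makes the label 'week 10' cover quite different situations. One patient may still be in an early calorie step, while another has been off the diet for a month. Only the experimental arm changes diet state, so this mixing does not cancel in the between-arm difference.

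The overlap adds a second problem. One patient's compliant week-10 value can be taken later in treatment than another patient's compliant week-16 value, yet the models treat the two as distinct, ordered time points. At stake is what the week-10 results describe: the effect at the end of the diet, or an average over days 40-100.

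**Working it through.** **Inputs.** Visit weeks 10, 16, 26 and 52 and the ±30-day windows are from the Study Flowchart. Diet length is from Section 2.4 and the diet steps from Appendix 2. Days are counted from the start, with nominal day = 7 × week. The protocol states no expected week-10 loss, so there is no figure of its own to reproduce on this point.

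**1. Windows and overlap**
- Week 10: 7 × 10 = 70; 70 ± 30 = days 40-100.
- Week 16: 7 × 16 = 112; 112 ± 30 = days 82-142.
- Nominal spacing: 112 − 70 = 42 days, less than 30 + 30 = 60, so the windows must overlap.
- Shared days: 82-100, that is 100 − 82 + 1 = 19 days.
- Week 26: 182 ± 30 = days 152-212, which starts after day 142. Week 52: 364 ± 30 = days 334-394. Neither overlaps a neighbour.

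**2. Week-10 window against the diet**
- Diet steps: 800 kcal, days 0-28; 1000 kcal, days 28-42; third level, days 42-56; fourth level, days 56-70.
- Day 40 lies in the 1000 kcal step, with 70 − 40 = 30 days of diet left.
- Day 100 is 100 − 70 = 30 days into Phase 2.
- Half of the window (30 of 60 days) is on the diet and half is off it.

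**3. Week-16 window against the diet**
- 82 − 70 = 12 and 142 − 70 = 72. Every in-window week-16 visit is 12-72 days after the diet, and all fall before day 182, inside Phase 2.

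**4. Illustrative size at the early edge**

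Assumption, not in the protocol: the experimental arm loses 8-10% by week 10.
- Linear loss: the share still to come at day 40 is 30/70 = 43%, so the shortfall is 0.429 × 8 to 0.429 × 10 = 3.4-4.3 points.
- Loss proportional to energy deficit, with assumed maintenance needs of 2000-2500 kcal/day and the women's steps (800, 1000, 1200, 1500 kcal):
  - At 2000: total deficit = 28×1200 + 14×1000 + 14×800 + 14×500 = 65,800. By day 40 it is 33,600 + 12×1000 = 45,600, or 69%.
  - At 2500: total = 28×1700 + 14×1500 + 14×1300 + 14×1000 = 100,800. By day 40 it is 47,600 + 12×1500 = 65,600, or 65%.
  - Share still to come: 31-35%, so the shortfall is 0.307 × 8 to 0.349 × 10 = 2.5-3.5 points.
- Range over both models: about 2.5-4.3 points for a patient seen on day 40.

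No matching figure can be given for the late edge, because the documents do not say how weight moves after the diet.

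**5. Width that avoids overlap**
- With week 16 left at ±30, the late limit of week 10 must be below day 82, so at most +11 days.
- With equal windows at both visits, the widest half-width without shared days is 20 (70 + 20 = 90; 112 − 20 = 92).
- ±7 days gives days 63-77, clear of day 82.

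**The case against.** The defence has several good points.

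- **Week 16.** A reader might infer that the week-16 comparison also mixes diet states. The flowchart does not support this. All in-window week-16 visits are post-diet with both arms on the same scheduled treatment, and only time since the diet varies. Appendix 3 starts the post-diet lifestyle programme after three months (about day 91), which falls inside both windows. The flowchart, however, shows lifestyle contacts from the start. That is a separate inconsistency to reconcile and not evidence for mixed states at week 16.
- **Order within a patient.** The window arithmetic alone would allow a patient's V9 to come after the same patient's V12. They are consecutive visits in successive phases, so this is unrealistic. The overlap matters between patients.
- **Timing bias by arm.** The trial is unblinded, and one might suspect that visits drift differently in the two arms. Both arms share the same schedule and windows, and nothing in the protocol predicts a difference.
- **Size.** The 2.5-4.3 points apply to one patient at the extreme edge. They would be a shift in the arm mean only if every experimental patient came on day 40. Comparator patients are losing weight too, so early visits in both arms partly cancel. Similar timing scatter in both arms mostly adds noise. With visits uniform over the window, the SD of timing is 60/√12 = 17.3 days. At 0.8-1.0 point per week, an SD of 5.3 rises to about 5.7-5.9.
- **Importance.** The endpoints are secondary and the secondary objective is descriptive. The primary t-test uses week-10 weight only as an imputation predictor.

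All of this limits the point without removing it. It might also be said that analysis windows belong in the statistical analysis plan. Such rules can relabel or exclude values, but they cannot produce an end-of-diet reading for a patient seen on day 40 or day 100. The visit window is stated in the protocol and has to be corrected there.

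**Conclusion.** The point holds for week 10 and for the separation of weeks 10 and 16. The overlap of 19 days and the straddle of 30 days on each side of the end of the diet follow directly from the flowchart and Appendix 2 and need no assumption. The week-10 contrasts in weight loss, 5% and 10% responders, glucose, lipids and blood pressure therefore pool on-diet and post-diet experimental-arm patients.

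The effect on the estimates is uncertain. The 2.5-4.3 points rest on an assumed 8-10% loss by week 10 and on either a linear or a deficit-based course, and they describe the edge of the window, not the expected bias. A reader might go further and infer that the primary week-26 result is compromised. The documents do not support that: the overlap does not reach week 26, and the imputation route is minor. This should be corrected, but it does not threaten the main conclusion.

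**What to change.** In the Study Flowchart, change the V9 (week 10) window from ±30 to about ±7 days (days 63-77). The routine week-16 window can stay as it is, since day 77 is before day 82. This removes the overlap. It reduces the straddle of the end of the diet from 30 to 7 days each side but does not eliminate it, so the actual study day should be recorded at each visit. Values outside the window should stay in the analysis under their true day and be logged as deviations.

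V9 is study-specific, so its date should be easier to control than that of a routine visit; this is an inference from Section 4.5. The cost is one flowchart cell in an amendment, tighter booking of one visit and a few more recorded deviations. No treatment rule changes.
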